#### 7.2.5 *End of Study*

The study will end once 10 study patients have been included. We foresee that the end will be scheduled for 31st of December 2025.

## **8 Selection of Subjects**

### 8.1 Selection of Study Population

All patients undergoing thoracic surgery for a confirmed or suspected lung cancer.

### 8.2 Inclusion Criteria

Patient undergoing thoracic surgery for a confirmed or suspected lung cancer. All patients eligible for major surgery, as defined by a thoracic procedure, are considered eligible for participation in this trial.

### 8.3 Exclusion Criteria

1. Uncertainty of pre-operative diagnosis, exception is per-op frozen section analysis confirming malignity
2. ASA  $\geq 3$
3. Bleeding disorders
4. Contraception/Pregnancy Avoidance

The aspiration of bone marrow will not impact contraception/pregnancy avoidance.

## **9 Screening**

### 9.1 Screening and Enrollment

All patients undergoing thoracic surgery will be screened pre-operative by the principal investigator. When eligible, patients will be asked for their participation and included after signing the informed consent.

## **10 Interventions/Treatment**

### 10.1 Intervention

- a. Blood sample collection during pre-operative blood collection  
A total of 12 ml will be collected
- b. Bone marrow aspiration during thoracic surgery  
Following the surgical intervention, bone marrow aspiration will be performed through the incisions made for the thoracic procedure. The ribs lying directly above and below the trocar incision will be exposed. A bone marrow needle will be advanced into the periost until the needle tip reaches the bone marrow. After removing the stylet a 2ml syringe will be attached to the aspiration needle and 0.5ml to 2ml of bone marrow will be aspirated before removing the needle. This procedure will be repeated twice for every trocar site, for a maximum of 3 trocar sites, or until 5ml of bone marrow aspirate is obtained. This part of the trial is experimental. Literature on rib bone marrow aspiration is scarce but good results are obtained. The procedures does not seem to be correlated with major AE.
- c. Lung tumor and adjacent healthy tissue collection – only tumor not used for diagnostic purposes.  
All surgical samples will be analyzed by our anatomopathological department. Viable and fresh material, obtained via true cut biopsy on the excised tissue and not used for the diagnostic purposes, will be collected by the LMCT.

All samples (blood, bone marrow, and fresh tumor tissue), will be transferred to the LMCT for immediate processing of viable cells (within 2 hours after isolation) and subsequent cultivation and/or cryopreservation for later usage.

## Randomization and Stratification

No randomization or stratification will be performed. All patients will be included in a consecutive manner.

### 10.2 Prohibited Medication

All anti-coagulants should be interrupted before the procedure as is standard practice for thoracic surgery.

### 10.3 Known Undesirable Effects of costal rib aspiration

- Pain
- Bleeding
- Infection

In a survey of members of the British Society of Haematology reported in 2003, there were 26 adverse events, including one fatality, out of an estimated total of 55,000 bone marrow biopsy procedures (0.05 percent). A follow-up survey of this group, reported in 2006 involving 20,323 procedures, resulted in the reporting of 15 adverse events (0.07 percent). Previous research evaluating the feasibility to detect disseminated tumor cells in bone marrow aspirate from the ribs couldn't identify any adverse events related to the bone marrow aspiration.

## **11 Study Assessments and Procedures**

### 11.1 Study Assessments

#### *11.1.1 Screening*

All patients undergoing thoracic surgery for lung cancer will be screened by the principal investigator for inclusion in this trial.

#### *11.1.2 Baseline*

Baseline screening consists of the pre-operative assessment for all patients undergoing thoracic surgery: blood tests (including coagulation testing), CT or PET CT, as well as consulting an anesthesiologist. No additional tests are required for this trial.

#### *11.1.3 Treatment Period*

- a. Blood sample collection during pre-operative blood collection  
A total of 12ml (3 EDTA tubes) will be collected
- b. Bone marrow aspiration during thoracic surgery  
Following the surgical intervention, a bone marrow aspiration will be performed through the incisions made for the thoracic procedure. The ribs lying directly above and below the trocar incision will be exposed. A bone marrow needle will be advanced into the periost until the needle tip reaches the bone marrow. After removing the stylet, a 2ml syringe will be attached to the aspiration needle and 0.5ml to 2ml bone marrow will be aspirated before removing the needle. This procedure will be repeated twice for every trocar site, for a maximum of 3 trocar sites, or until 5ml of bone marrow aspirate is obtained.
- c. Lung tumor collection – only tumor not used for diagnostic purposes.  
All surgical samples will be analyzed by our anatomopathological department. Viable and fresh material, obtained via true cut biopsy on the excised tissue and not used for the diagnostic purposes, will be collected by the LMCT.

#### 11.1.4 Follow-Up

All patients are hospitalized one day prior to surgery. After surgery, patients will stay in the post-anesthesia care unit (PACU) for one night. Following surgery, the patients will stay in the hospital for 5-7 days. All patients will be seen by their surgeon at the consultation 2 weeks following surgery. We don't expect a prolonged hospital stay or additional hospital visits will be necessary for the patients partaking in the trial.

#### 11.1.5 End of Study

Adverse events will be followed up to four weeks postoperatively.

#### 11.1.6 Re-screening

No

#### 11.1.7 Early Termination

The trial will be ended prematurely if grade 3 (or higher) adverse events occur in 2 patients

#### 11.1.8 Unscheduled Visits

Not expected

### 11.2 Assessment Types

#### 11.2.1 Efficacy Assessment

In accordance with a recent single-cell analysis study on patient-derived bone marrow, we will process blood and bone marrow specimens from patients within two hours of collection. The bone marrow mononuclear cells (BM-MNCs) will subsequently be isolated by density centrifugation using LSM Lymphocyte Separation Medium (#50494X, MPbio). In short, the bone marrow will be diluted twofold using phosphate-buffered saline (PBS), layered on top of 1 volume LSM Lymphocyte Separation Medium in a 50-ml Falcon tube, and centrifuged at 2300 rpm for 25 minutes at room temperature without brake. Next, the MNC layer will be isolated and washed with PBS after lysis of red blood cells with RBC lysing buffer. To count and purify the Lin- CD34+ HSPCs per patient using our BD FACS Aria™ III Cell Sorter, BM-MNCs will be stained with monoclonal antibodies for 30 minutes on ice: anti-Lineage antibody, anti-CD34 antibody, anti-CD45 antibody, and anti-Epcam antibody to divide each bone marrow sample over HSPCs (Lin/CD45/Epcam- CD34+), immune cells (Lin/CD34/Epcam- CD45+), disseminated cancer cells (CD45/CD34- Epcam+) and the rest fraction.

The endpoint will be the determination of viable HSPC numbers per sample as well as detection of disseminated Epcam+ NSCLC cells. For future experiments we aim at a minimum of **2x10E6 Lin- CD34+ HSPCs** to allow single-cell sequencing ( $10^6$ ), bone marrow cultivation ( $5 \times 10^5$  cells per culture), and transplantation in immunodeficient mice ( $10^5$  cells per injection).

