## 1 Trial Registration/Protocol Summary

Information	
EudraCT number:	N/A
Date of registration:	
ClinicalTrials.gov:	NCT05251805
Official Title:	Phase I clinical trial evaluating the safety and feasibility of bone marrow aspiration from ribs during thoracic surgery
Study Phase/Type:	Phase I clinical trial
Condition:	Lung cancer
Objectives:	Evaluate the safety and feasibility of bone marrow aspiration during thoracic surgery
Investigational Product or Medical Device:	None
Interventions:	
 
1. Pre-operative blood sample collection
 
2. Costal bone marrow aspiration
 
3. Lung tumor and adjacent tissue sampling
 

Endpoints:	
 
1. Safety: the occurrence of complications
 
2. Feasibility: Obtain a minimum of <math>2 \times 10^6</math> Lin CD34+ Hematopoietic Stem and Progenitor Cells (HSPCs) to allow single cell RNA sequencing (<math>10^6</math>), bone marrow cultivation in vitro (<math>5 \times 10^5</math> cells per culture) and transplantation in immuno-deficient mice (<math>10^5</math> cells per injection).
 

Study population:	Lung cancer patients undergoing thoracic surgery
Number of patients:	10
Overview of study design:	Phase I feasibility trial
Statistical Considerations:	None
Sponsor:	UZ Brussel
Inclusion Criteria:	Confirmed or suspected lung cancer patients undergoing thoracic surgery
Exclusion Criteria:	
 
1. ASA <math>\geq 3</math>
 
2. Bleeding disorders
 

Target Date of first enrolment:	01/10/2022
Target sample size:	10

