## 5.4 Study Rationale and Purpose

In general, antitumor immunotherapy tends to spark the patients' own tumor-specific effector T cells to multiply, recognize and kill tumor cells. Yet, a typical characteristic of immunotherapy-resistant (lung) tumors' deceptive gambit, is their molding of an effector T-cell hostile **tumor microenvironment (TME)**. The latter comprises cellular, molecular, vascular, and physical **barriers** for effector T cells which hamper effective tumor cell killing. With regard to the cellular barriers, we and others have appointed a leading role to the immunosuppressive myeloid cells. These myeloid cells represent a heterogeneous group of subsets with embryonic origin (macrophages) and/or hematopoietic origin (dendritic cells, macrophages, granulocytes, mast cells, and platelets), suggesting that the **bone marrow niche (BMN)** is involved in the creation of an immunosuppressive T-cell hostile TME. Moreover, this niche has been shown to aid in pre-metastatic niche formation while it has also been proposed as a supportive **hideout** for disseminated cancer cells, as reported by the detection of Epcam+ CD45 disseminated cancer cells in 43,5% of sternal aspirated BM samples from 62 NSCLC patients. Nevertheless, as BM aspiration is a painful process and therefore, unlike blood drawing not routinely performed, it remains a tremendously **understudied niche in solid cancers**.

Next to the fundamental information that BMN investigation would deliver to ameliorate our understanding of NSCLC progression and resistance to (immuno)therapy, bone marrow represents an extremely valuable biomaterial for preclinical onco-immunology research. More specifically, the Lin- CD34+ hematopoietic stem (and progenitor) cells or **HSPCs** have been used to **generate humanized mice** by transplanting total body irradiated mice with human bone marrow. Anti-tumor immunotherapy (and research thereof) relies on histocompatible cell-to-cell interactions between the immune system, tumor cells and their TME. Hence, humanized patient-derived xenograft models in which the immune system and tumor are derived from the same patient, a.k.a. 'murinized patients', represent the ultimate model to study human tumor immunology and evaluate innovative immunotherapies.

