### 6.4 Endpoints

1. Safety: the occurrence of complications
2. Feasibility: Obtain a minimum of  $2 \times 10^6$  Lin- CD34+ HSPCs to allow single cell sequencing ( $10^6$ ), bone marrow cultivation ( $5 \times 10^5$  cells per culture) and transplantation in immunodeficient mice ( $10^5$  cells per injection).

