## **7 Investigational Plan**

### 7.1 Overall Study Design

- 1) This trial is a phase I feasibility trial. It is designed to evaluate the feasibility and safety of obtaining bone marrow upon costal aspiration during surgery.
- 2) If feasibility and safety of rib bone marrow aspiration are confirmed in this pilot trial, a large-scale study will be started to optimize and conduct fundamental and translational research via the X-talk project and RADar project (see details under 5.4, page 9).

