#### 13.1.2 Interim analysis

After the inclusion of the first 5 patients, an interim analysis will be performed to confirm whether the size of the blood sample is adequate, how much bone marrow is extracted and whether this is adequate to do the lab analysis.

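### The 2x10^6 feasibility minimum is set on Lin- CD34+ HSPCs, but the sorting gate also requires CD45-, so the gated count can only equal or fall below the count the endpoint describes

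*Protocol*

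**What the plan says.** The endpoint definition is the same wherever it appears. The summary in section 1 sets a minimum of 2x10^6 Lin- CD34+ cells, described as "Hematopoietic Stem and Progenitor Cells (HSPCs) to allow single cell RNA sequencing". Section 6.4 repeats it: "Lin- CD34+ HSPCs to allow single cell sequencing". Section 5.4 identifies the population by the same two markers: "the Lin- CD34+ hematopoietic stem (and progenitor) cells or" HSPCs. The closing sentence of 11.2.1 restates the target: "For future experiments we aim at a minimum of 2x10E6 Lin- CD34+ HSPCs". None of these carries a CD45 or Epcam condition.

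The measurement is in section 11.2.1. The sorter is used "To count and purify the Lin- CD34+ HSPCs per patient", with staining for lineage markers, CD34, CD45 and Epcam. The same sentence then gives the gates: "to divide each bone marrow sample over HSPCs (Lin/CD45/Epcam- CD34+), immune cells (Lin/CD34/Epcam- CD45"+), followed by disseminated cancer cells (CD45- CD34- Epcam+) and a rest fraction for everything else. The endpoint is the number of viable HSPCs per sample.

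Two later steps bear on this. The interim look after 5 patients (section 13.1.2) asks "how much bone marrow is extracted and whether this is adequate to do the lab analysis". Section 7.1 states: "If feasibility and safety of rib bone marrow aspiration are confirmed in this pilot trial, a large-scale study will be started".

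**The concern.** The protocol gives two definitions of the cell it counts, and they differ by a marker. In sections 1, 5.4 and 6.4 an HSPC is Lin- CD34+. In the gate it is Lin- CD34+ CD45- Epcam-.

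Excluding Epcam+ events has an evident reason, since Epcam is the protocol's marker for tumour cells. No reason is given for CD45-. Nor can it be taken as already covered by Lin-: the protocol's own immune gate is Lin- CD45+, so its scheme allows a cell to be Lin- and CD45+ at once.

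The HSPC count is the only feasibility endpoint in section 6.4, in a trial of 10 patients with no statistical analysis planned, so the result is read straight from the counts. If the gate is narrower than the endpoint, the count can miss cells that the endpoint wording includes. Those cells also leave the purified fraction meant for sequencing, culture and transplantation.

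**Working it through.** **Inputs, all from the protocol**

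- Threshold: 2x10^6 Lin- CD34+ HSPCs (sections 1, 6.4 and 11.2.1).
- Uses: 10^6 for sequencing, 5x10^5 per culture, 10^5 per injection (section 6.4).
- Gates: as listed in section 11.2.1. The minus sign is read as covering the whole slash list before it. The immune-cell and cancer-cell entries are written the same way and make sense only on that reading.

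**Step 1. The plan's own figure.** One use of each kind needs 10^6 + 5x10^5 + 10^5 = 1.6x10^6 cells. One culture and five injections give 10^6 + 5x10^5 + 5 x 10^5 = 2.0x10^6. The threshold is compatible with the listed uses but is not fixed by them, because the numbers of cultures and injections are not stated. The point here does not depend on this.

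**Step 2. Where each cell goes.** Four markers, each positive or negative, give 2^4 = 16 patterns.

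| Fraction | Condition as written | Patterns |
|---|---|---|
| HSPC | Lin- CD45- Epcam- CD34+ | 1 |
| Immune | Lin- CD34- Epcam- CD45+ | 1 |
| Cancer cells | CD45- CD34- Epcam+ (Lin either) | 2 |
| Rest | all others | 12 |

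No pattern falls in two gates. The endpoint wording (Lin- CD34+, any CD45, any Epcam) covers 4 patterns, and the gate covers 1 of these. The other 3 all fall in the rest fraction, because the immune and cancer-cell gates require CD34-.

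**Step 3. The CD45 condition alone.** With Epcam- held fixed, 2 patterns meet Lin- CD34+: CD45- and CD45+. The gate counts the first and sends the second to the rest fraction.

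**Step 4. Direction.** The gate is a strict subset of the endpoint population, so gated count <= endpoint count in every sample. They are equal only if no Lin- CD34+ cell is CD45+ or Epcam+. This follows from set inclusion and needs no outside figure.

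**Step 5. Size, by assumption.** Let g be the share of Lin- CD34+ Epcam- cells that are CD45+. The protocol gives no value, so g is varied. A sample with 2x10^6 such cells is counted as 2x10^6 x (1 - g). To reach 2x10^6 on the gate, a sample must hold 2x10^6 / (1 - g).

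| g (assumed) | Counted from 2x10^6 | Needed for 2x10^6 on the gate |
|---|---|---|
| 0 | 2.0x10^6 | 2.0x10^6 |
| 0.10 | 1.8x10^6 | 2.2x10^6 |
| 0.25 | 1.5x10^6 | 2.7x10^6 |
| 0.50 | 1.0x10^6 | 4.0x10^6 |

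**Step 6. Does dropping CD45- cause overlap?** With the HSPC gate set to Lin- CD34+ Epcam-, the pattern counts are HSPC 2, immune 1, cancer cells 2, rest 11, with no overlaps. The one pattern that moves from rest to HSPC is Lin- CD34+ CD45+ Epcam-.

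**The case against.** The strongest reply is that Lin- CD34+ is a short label and the bracket in 11.2.1 is its operational form. One sentence says the sorter counts and purifies these cells and then spells out the gate. Only one count is described, and the same gated fraction is both counted and sorted. On that reading nothing is understated, and only the label needs completing. The stricter gate also errs on the cautious side, since it cannot overclaim feasibility.

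Part of this stands. The sponsor may intend CD45-, and the documents do not exclude it. No value of g is given, so it cannot be shown that any of the 10 patients would be classified differently. The interim look does not cite 2x10^6, and section 7.1 gives no numerical rule for feasibility being confirmed, so no written decision rule is shown to flip.

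The rest does not stand. The protocol nowhere says that the label stands for the full gate, and section 5.4 names HSPCs by Lin- CD34+ alone. The Lin- CD45+ immune gate shows that the CD45 condition is additional. The composition of the lineage stain and the cut-offs can be left to a laboratory procedure. Two marker definitions that disagree inside the protocol are a different matter. A cautious error still counts when the trial's purpose is to learn whether enough cells can be obtained, and it diverts cells from the planned uses.

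**Conclusion.** The concern holds. The endpoint and the gate define different populations, and the gate is the narrower one. A sample can meet the section 6.4 wording and fall below 2x10^6 on the gate, but not the reverse.

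The direction rests only on the marker definitions and on reading the minus sign across each slash list. The size is unknown and may be nil; the assumed range of g from 0 to 50% gives counts from 2.0x10^6 down to 1.0x10^6 and shows scale only. This should be corrected before per-patient feasibility is read. Confidence is medium, because the sponsor's intent on CD45 and the share of CD45+ cells are not stated.

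**What to change.** Use one marker definition in sections 1, 6.4 and 11.2.1, and apply it to both the count and the sort, so that the cells counted are the cells available for the planned uses. There are two ways to do this:

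- **Match the stated endpoint.** Remove CD45- from the HSPC gate, leaving Lin- CD34+. Keep Epcam- only if it is also written into sections 1 and 6.4. CD34 already separates this gate from the immune and cancer-cell gates.
- **Keep CD45-.** Write the full marker string into sections 1 and 6.4, and report the number of Lin- CD34+ CD45+ cells from the same run beside the HSPC count, so that the effect of the condition is visible for each patient.

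The cost is wording in three sections and, under the first option, one gate setting. The stain and sort run are unchanged, and no extra sample or patient is needed.

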#### 11.2.2 Safety and Tolerability Assessments

- NRS pain score: The NRS pain score will be used to evaluate postoperative pain. Bone marrow aspiration will be performed at a maximum of 3 trocar sites. Thoracic procedures are known as painful procedures mandating multimodal pain treatment. Bone marrow aspiration is not expected to add to the pain experience.
- Bleeding: in all patients undergoing a thoracic procedure a thoracic drainage system is used and all patients will stay at the recovery ward following surgery. Since the bone marrow aspiration is done under visual control we don't expect any significant postoperative bleeding.
- Infection: the bone marrow aspiration is done under sterile conditions, using the incisions made to introduce the trocars. Follow-up is provided 14 days following surgery.

### 11.2.3 *Laboratory Evaluation*

Hematology: a preoperative coagulation screening will be performed for all patients; this is the standard procedure for all patients undergoing thoracic surgery.

## **12 Safety Monitoring and Reporting**

### 12.1 Adverse Events

#### 12.1.1 *Definitions and Reporting*

All Adverse events will be graded according to the Clavien Dindo classification system:

Grade	
1	Any deviation from the normal postoperative course without the need for pharmacological treatment or surgical, endoscopic and radiological interventions. Acceptable therapeutic regimens are: drugs as antiemetics, antipyretics, analgetics, diuretics and electrolytes and physiotherapy. This grade also includes wound infections opened at the bedside.
2	Requiring pharmacological treatment with drugs other than such allowed for grade I complications. Blood transfusions, antibiotics and total parenteral nutrition are also included.
3	Requiring surgical, endoscopic or radiological intervention
3a	Intervention under regional/local anesthesia
3b	Intervention under general anesthesia
4	Life-threatening complication requiring intensive care/intensive care unit management
4a	Single organ dysfunction
4b	Multi-organ dysfunction
5	Patient demise

Clavien Dindo classification system

#### 12.1.2 *Reporting Period*

All adverse events related to the bone marrow aspiration will be evaluated and classified by their treating physician. Adverse events occurring during the first postoperative month (30 days) will be registered.

### Serious Adverse Events

#### 12.1.3 *Definitions*

All adverse events of grade 3 or higher (according to the Clavien Dindo classification) will be reported as serious adverse events.

#### 12.1.4 *Immediate Reporting*

In the occurrence of adverse events of grade 3 or higher related to the trial procedure, the ethical committee will be contacted. In the occurrence of 2 adverse events of grade 3 or higher the trial will be prematurely discontinued.

## 12.2 Suspected Unexpected Serious Adverse Events (SUSAR)

### 12.2.1 Definitions

All adverse events of grade 3 or higher (according to the Clavien Dindo classification) that might be related to a trial related procedure will be reported as a serious adverse event

### 12.2.2 Reporting

In the occurrence of adverse events of grade 3 or higher related to the trial procedure, the ethical committee will be contacted. In the occurrence of 2 adverse events of grade 3 or higher the trial will be prematurely discontinued and the ethical committee will be notified.

## 12.3 Procedures for Handling Special Situations

### 12.3.1 Pregnancy

Pregnancy is no contra-indication for participating in the trial, however due to the context of the underlying disease we don't expect to include any pregnant patients.

